4.4 Handling of missing safety indicators

The missing values of safety evaluation indicators were filled by the method of Worst Observational Data Carryover (WOCF).

According to the conservative principle, if the severity of an AE is missing, it will be recorded as "grade 3" in the summary description, and if the relationship between an AE and the investigational medical device is missing, it will be recorded as "probable" in the summary description as "probable".

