4.5 Criteria for passing/failing clinical trial results

The target value of the main effectiveness evaluation index (tumor disease control rate) of the trial was 80%, and if the lower limit of the 95% confidence interval of the test results was greater than 80%, the tumor disease control rate of the experimental group reached the target.

If the main safety evaluation index of the trial (the proportion of CTCAE grade 3 toxic reactions) is greater than 5%, the clinical trial fails.

If the trial has CTCAE grade 4 and 5 toxicity, the clinical trial fails.

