- (3) The missing values of DCR and primary safety evaluation indicators (proportion of CTCAE grade 3 toxicities, proportion of CTCAE grade 4 and 5 toxicities) at 3 months after the end of treatment can be estimated using worst-case scenarios.
- (4) The missing values of qualitative secondary effectiveness evaluation indicators ORR, DCR and long-term follow-up effectiveness evaluation indicators can be estimated using worst-case scenarios;
- (5) The missing values of quantitative secondary efficacy evaluation indicators DOR, tumor markers, product ease assessment and long-term follow-up effectiveness evaluation indicators were not estimated.
- (6) Erroneous, unreasonable data (out-of-range data and data that contradicts other data or indicators of the study protocol) can be treated as missing values;
- (7) Worst-case estimates are used for missing values for all minor safety indicators;

- (8) The sensitivity analysis of the main effectiveness evaluation indicators and main safety evaluation indicators after treatment was carried out in the whole analysis center.
- (9) The sensitivity analysis of all secondary effectiveness evaluation indicators after treatment was carried out in the whole analysis center.
- (10) For all secondary safety evaluation indicators after treatment, sensitivity analysis was carried out in the security dataset.

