2.2 Safety evaluation index

2.2.1 Key safety indicators

- **Proportion of CTCAE grade 3 toxicity**

Proportion of subjects with grade 3 toxicity in the trial cycle.

Calculation formula: Proportion of CTCAE grade 3 toxicity = number of subjects with CTCAE grade 3 toxicity in the test cycle / total number of subjects $\times 100\%$;

- **Proportion of CTCAE grade 4 and 5 toxicity**

Proportion of participants with grade 4 and 5 toxicity during the trial cycle.

Calculation formula: Proportion of CTCAE grade 4 and 5 toxicity = number of subjects with CTCAE grade 4 and 5 reactions in the trial cycle / total number of subjects $\times 100\%$;

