5.5.1 Proportion of CTCAE toxicity

The severity of AEs was assessed according to Common Adverse Event Common Terminology Criteria (CTCAE) V5.0.

Grade 1: mild, asymptomatic or mildly symptomatic, clinical or diagnostic findings only, no treatment required;

Level 2: moderate, minimal, localized, or non-invasive interventions, age-related limitations in instrumental activities of daily living (ADLs) (instrumental ADLs refer to cooking, grocery or clothing shopping, phone access, financial management, etc.);

Grade 3: severe or medically significant, but not immediately life-threatening, hospitalization or prolonged hospital stay, disability, restriction of self-care ADL (self-care ADL refers to bathing, dressing and undressing, eating, toileting, taking medications, not being bedridden);

Grade 4: life-threatening; requiring urgent intervention;

Grade 5: AE-related death.

The number and percentage of subjects who achieved each grade of CTCAE toxicity were calculated, and the details of toxicity were described in a table.

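### SAP 4.4 grades every adverse event of missing severity as 3, which is not the worst case when any grade 4 or 5 toxicity fails the trial

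*SAP*

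**What the plan says.** **Default grade.** SAP 4.4 invokes a conservative principle and states that "if the severity of an AE is missing, it will be recorded as 'grade 3' in the summary description". It makes no exception for outcome or seriousness. A companion default covers causality: "if the relationship between an AE and the investigational medical device is missing, it will be recorded as 'probable' in the summary description".

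**Pass/fail rules.** Protocol 4.5 has two safety rules:
- Grade 3: if "the proportion of CTCAE grade 3 toxic reactions) is greater than 5%, the clinical trial fails".
- Grades 4 and 5: "If the trial has CTCAE grade 4 and 5 toxicity, the clinical trial fails". Protocol 3.1.2 and SAP 1.2 give 0% as the acceptable value.

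**How the proportions are counted.** SAP 2.2.1 defines the grade 3 proportion as "number of subjects with CTCAE grade 3 toxicity in the test cycle / total number of subjects", and the grade 4/5 proportion in the same way. SAP 5.5.1 plans the analysis: "The number and percentage of subjects who achieved each grade of CTCAE toxicity were calculated", with toxicity details in a table. It defines grade 4 as life-threatening or requiring urgent intervention, and grade 5 as AE-related death.

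**Other missing-data rules in reach.** The sentence just before the default grade in SAP 4.4 fills missing safety indicators by worst observation carried forward (WOCF). Protocol 4.7.2 item (3) says that missing values of the primary safety indicators, including the "proportion of CTCAE grade 4 and 5 toxicities) at 3 months after the end of treatment can be estimated using worst-case scenarios". No text ranks these rules for an event that was recorded but not graded.

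**The concern.** A conservative default should not make the result look better than the truth. This one can. Grade 3 is the worst case only for the 5% rule. For the zero-tolerance rule it is the most severe grade that does no harm. The rule therefore favours the device on the stricter of the two safety criteria, and an event that should end in failure can be counted as one tolerated grade 3 subject.

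The same sentence can also work against the device. An ungraded minor event is promoted to grade 3, and the 5% limit allows only two such subjects out of 47.

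So a code assigned for lack of data, rather than an observed toxicity, could settle a primary safety criterion in either direction.

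**Working it through.** **Inputs.** N = 47 enrolled (Protocol 4.2.1, SAP 1.4), with 42 evaluable as the planning figure. The grade 3 limit is a proportion above 5%, judged on the point estimate; the grade 4/5 limit is any occurrence (both Protocol 4.5). The safety set is everyone treated at least once with at least one safety assessment (SAP 3), so its size is 47 only if all enrolled subjects qualify.

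**Step 1. Reproduce the denominator.** With target 80%, expected rate 95%, two-sided 0.05 and power 80%:

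n = [(1.960·√(0.80·0.20) + 0.842·√(0.95·0.05)) / 0.15]² = 41.6, so 42. Then 42 / 0.90 = 46.7, so 47. The plan's figures are confirmed.

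**Step 2. Where the grade 3 rule turns.**

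| Subjects with grade 3 | N = 47 | N = 42 |
|---|---|---|
| 1 | 2.1% pass | 2.4% pass |
| 2 | 4.3% pass | 4.8% pass |
| 3 | 6.4% fail | 7.1% fail |

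Three is the smallest failing count for any safety set of 40 to 59 subjects. At 38 or 39, two already fail. Each subject with an observed grade 3 event reduces by one the number of default-graded subjects needed to fail.

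**Step 3. One ungraded event that was truly grade 4, no other events of grade 3 or above, N = 47.**

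| Rule applied | Grade 3 | Grade 4/5 | Verdict |
|---|---|---|---|
| SAP 4.4 default | 1/47 = 2.1% | 0/47 | both pass |
| Correct grade | 0/47 | 1/47 = 2.1% | fail |
| Protocol 4.7.2(3), worst case read as grade 4/5 | 0/47 | 1/47 = 2.1% | fail |

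WOCF depends on what else was observed in the subject. If it is read as carrying the worst grade already recorded, a subject whose other events were grade 1 or 2 would get at most grade 2, which counts towards neither criterion.

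**Step 4. Can a chance be put on the opposite error?** The documents give neither the number of AEs per subject nor the rate of missing severity. Assume k AEs per subject, severity missing independently with probability m, every ungraded AE counted as a toxicity, and no observed grade 3 event. Then q = 1 − (1 − m)^k is the chance that a subject has at least one default grade 3, and the number of such subjects is binomial(47, q). The chance of three or more is:

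| m | k = 1 | k = 5 |
|---|---|---|
| 0.1% | below 0.01% | 0.2% |
| 0.5% | 0.2% | 11% |
| 1% | 1.2% | 41% |
| 2% | 6.8% | 84% |

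For example, k = 5 and m = 1% give q = 1 − 0.99⁵ = 0.049 and a chance of 0.407. The answer runs from near 0 to 84% and is set by the assumptions, not by the plan.

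**The case against.** **The event will be caught.** Protocol 3.1.5.1 has investigators grade recorded AEs by CTCAE V5.0. Protocol 4.7.2 has missing data discussed and settled by investigators and biostatisticians at the data review. SAP 5.5.4 lists each AE and SAE with its severity, so a fatal SAE shown as grade 3 would be visible. This stands as a reason why a silent miss is unlikely. It does not supply a coding rule for an event still ungraded after review, and the written rule points to grade 3.

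**A death already has a grade.** SAP 5.5.1 defines grade 5 as AE-related death, so an analyst could grade a related death from its outcome. This stands in part. A reader might infer that an ungraded fatal event necessarily escapes the zero-tolerance rule; the documents do not support that, because the definition offers a way to grade it. But SAP 4.4 makes no such exception and nothing tells the programmer to derive grade from outcome. Grade 4 also has a definition in SAP 5.5.1, but there the fact that fixes the grade is a judgement about the threat to life, less plain than a death.

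**The Protocol's worst-case rule may govern.** If it does, and is read as grade 4/5, nothing escapes. But it is permissive (it says missing values can be so estimated), and it may be meant for missing subject-level values rather than an ungraded event. What stands is that precedence is unresolved, so escape is possible, not certain.

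**The rule covers only a summary description.** The summary by grade is the only planned analysis of the primary safety indicators, so the natural reading is that it feeds the verdict. If that is not intended, the SAP should say so.

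**Over-counting minor events is what a conservative default does.** This is fair. It works against the sponsor, and a reporting row is enough to expose it.

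**Conclusion.** The point holds in this form: the grade 3 default is not conservative for the grade 4/5 criterion, and the plan does not say which of three rules governs an ungraded AE. One ungraded life-threatening event is enough to turn a failure into a pass (1/47 = 2.1% grade 3 and 0/47 grade 4/5). A fatal event could do the same unless it is graded from the SAP 5.5.1 definition. In the other direction, the third default-graded subject among 47 fails the trial if no grade 3 event was observed, and fewer suffice otherwise.

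This rests on three assumptions: the safety set is about 47, the summary by grade decides the two criteria, and an ungraded AE counts as a toxicity. On the last, neither document says whether a toxicity must be device-related. An AE that also lacks a causality rating would be treated as probably related.

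A reader might take the top of the range in step 4 as the likely risk of failure by default codes. The documents do not support any single figure there: both inputs are assumed, and the chance falls to near 0 if few severities are missing. The case for change rests on the stated rule and on thresholds that one to three subjects can cross, not on a predicted frequency.

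**What to change.** Amend SAP 4.4 before database lock.

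1. For an AE still ungraded after the pre-lock data review, count a fatal outcome as grade 5, an event recorded as life-threatening or needing urgent intervention as grade 4, and all others as grade 3.
2. State that for ungraded AEs this rule takes precedence over the WOCF sentence and over the worst-case option in Protocol 4.7.2(3).
3. Report both primary safety proportions with and without default-graded events, and state whether the pass/fail verdict changes.

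Item 1 keeps grade 3 for minor ungraded events, so it does not remove the upward error. Item 3 makes that error visible.

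The cost is a few sentences, one extra table row, and a grade 4/5 result that may be less favourable if an ungraded event proves to be fatal or life-threatening. No treatment, visit or sample size changes.

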4.5 Missing processing of other data

If other data are missing, a footnote will be provided under the statistical analysis table if there is a special note to fill in the summary.

5 Methods of statistical analysis

5.1 Statistical software

Statistical Analysis System (SAS) version 9.4 was used for programmatic analysis.

5.2 General principles

In general, continuous variables will be statistically described using the number of cases, arithmetic mean, standard deviation, median, 25% quantile (Q1), 75% quantile (Q3), minimum and maximum values, etc., while categorical variables will be statistically described using frequency, frequency, incidence, and composition ratio. Unless otherwise specified, all statistical tests will be performed using a two-sided test of $\alpha=0.05$ to calculate a two-sided 95% confidence interval.

Unless otherwise specified, the following conventions will be followed for the retention of decimal places

in this statistical analysis:

Table 3 Data decimal place retention provisions

Statistics	Decimal place provisions
Arithmetic mean, median, Q1, Q3	1 decimal place more than the actual number of decimal places.
standard deviation	1 decimal place more than the arithmetic mean and no more than 4 decimal places.
Minimum, maximum	Same as the actual number of decimal places.
Frequency, incidence, composition ratio	Keep 1 decimal place as a percentage, and the result with a frequency of 0 is "0", and the result is 100% of the display is "100".
Confidence limit	Metrological data: Same as arithmetic mean decimal places Counting data: 1 decimal place is kept as a percentage.
Test statistics (e.g., chi-square or t -value, etc.).	Keep 4 decimal places.
P -value	Keep 4 decimal places, and if the specific value is less than 0.0001, it will be represented as "<0.0001".

5.3 Subject characteristics

5.3.1 Distribution of participants

The number and percentage of subjects participating in screening, screening success, enrollment, completion of radiotherapy, completion of primary efficacy evaluation, completion of trial and early withdrawal, and each reason for withdrawal will be described throughout the trial.

5.3.2 Deviation from the protocol

Depending on protocol deviations and the specific situation, participants who are not included in FAS, PPS, or SS will be discussed at the data review meeting and identified prior to database locking.

The number, number and incidence of protocol deviations in each category are summarized and the list details the regimen deviations of the subjects.

5.3.3 Demographic characteristics and baseline data

Demographic data and baseline data will be analyzed based on FAS. The demographic indicators included gender and age, and the baseline data indicators included height, weight, vital signs, ECOG physical condition classification, and cardiac function classification, and the above indicators were summarized descriptively.

5.3.4 History of tumor treatment

The history of tumor treatment will be analyzed based on SS. Treatment history includes surgical treatment

history, radiation therapy history, interventional therapy history, cytotoxic drug treatment history, immunotherapy history, and targeted therapy history, and the above treatment history is summarized descriptively.

5.3.5 History of present tumor presentness

The history of present tumor will be summarized based on FAS. The indicators of present history of tumor include diagnosis basis, tumor type, tumor location, tumor status, pathological classification, and TNM stage. The frequency and composition ratio of the above categorical variables were calculated.

The list details the subject's present medical history.

5.3.6 Past medical history

A detailed description of the subject's past medical history was based on the SS list.

5.3.7 Prior/concomitant medications

Prior medication refers to medication taken prior to the first radiation therapy.

Prior/concomitant medications will be summarized based on SS. Prior/concomitant medications were coded using the World Health Organization Pharmacological Dictionary (WHODD) (version: 09/2021) according to pharmacology/therapeutics (ATC02).and Preferred Name (PN) classification, and the frequency and percentage of previous/concomitant medications were counted.

The list details the subject's previous/concomitant medications.

5.3.8 Concomitant therapy

A detailed description of the subject's concomitant treatment based on the FAS list.

5.3.9 Radiation therapy plan

Based on FAS, the radiotherapy plan was described and summarized, including the treatment cycle, the total dose of the target area of the radiotherapy plan, and the fractional dose. The list describes the radiotherapy plan design for each subject.

The list describes the dose limits for organs at risk.

To summarize the use of respiratory gating by participants in radiotherapy delivery.

5.4 Effectiveness evaluation indicators

5.4.1 Key Effectiveness Indicators

The primary effectiveness evaluation was based on the Full Analysis Set (FAS) and the Protocol-Consistent Set (PPS).

The number and percentage of cases that achieved tumor disease control at 3 months during the follow-up period were calculated, and the 95% confidence interval of tumor disease control rate was calculated by Clopper-

Pearson, and the target value of tumor local control rate was 80%, and if the lower limit of the 95% confidence interval of the test results was greater than 80%, the tumor local control rate was reached. The single-sample chi-square test was used to compare whether there was a statistical difference between the local control rate and the target value.

For the evaluation results of the imaging review team, if the efficacy evaluation results of the two evaluators are consistent, the final evaluation results of the two evaluators will be taken, and if the evaluation results of the two evaluations are inconsistent, the independent evaluation value of the third evaluator will be taken as the final evaluation results.

Based on FAS, the sensitivity analysis of the main effectiveness indicators was carried out, and the missing values of the main effectiveness evaluation indicators were filled by the method of Worst Observational Data Carryover (WOCF).

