3.1.2 Choice of trial method and justification

This trial was designed using the prospective, two-center, single-group target value method.

- (1) Prospective study: Adopt a research approach that traces from the present to the future. Prospective studies can establish cause and effect; There are unified diagnosis, detection and evaluation standards for the obtained data, so the data processing is controllable.
- (2) Single centers: Select 1 clinical trial institution to carry out the clinical trial.
- (3) Single-group target value method: Because the same device of the experimental medical device is radioactive and difficult to obtain, the existing treatment method is not feasible due to objective conditions, so the single-group target value method is adopted. Moreover, the applicable population and main evaluation indicators of experimental medical devices can be fully defined and relatively stable; The main evaluation index adopts the effective rate mentioned in the "Guidelines for the Technical Review of Clinical Evaluation of Proton Carbon Ion Therapy System" (CFDA Circular No. 4 [2018]), which is relatively objective and reproducible. According to the Guidelines for the Technical Review of Clinical Evaluation of Proton Carbon Ion Therapy Systems, the target value of therapeutic response rate for

experimental medical devices should be at least 80%, and the expected value should be 95%. Among them, the effective definition is: CR+PR+SD (complete response CR, partial response PR, disease stable SD), which is basically consistent with the definition of tumor disease control rate in this clinical trial. Therefore, no control group was set up in this clinical trial, and the single-group target value method was used to evaluate whether the tumor disease control rate reached the target value (80%) and the main safety evaluation index CTCAE 3 when ProBeam was used in radiotherapy for tumor patients. Whether the proportion of grade toxicities is less than acceptable (5%) and whether the proportion of CTCAE grade 4 and 5 toxicities is acceptable (0%).

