4.2 Sample size calculation

4.2.1 Total sample size

This clinical trial intends to enroll 47 subjects. The sample size determination process is as follows:

This clinical study is designed for clinical verification of a single group of target values, and the tumor disease control rate, the main effectiveness evaluation index, is used as the basis for sample size estimation. According to the Guidelines for the Review of Clinical Evaluation Technologies of Proton Carbon Ion Therapy System (CFDA Circular No. 4 of 2018), the target value is set at 80%, and the bilateral significance level is 0.05, and the power degree 80%, applying the sample size estimation professional software PASS 15.0, calculated by the above parameters, the test group needs a sample size of at least 42 cases. Considering that about 10% of cases may be dropped or lost to follow-up during clinical validation, the sample size of the experimental group was expanded to 47 cases.

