4.3 The level of significance and power of clinical trials

The significance level α (bilateral) = 0.05, and the power was 80%.

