2.1 Effectiveness evaluation indicators

2.1.1 Key Effectiveness Indicators

- **Tumor disease control rate (DCR) at 3 months after the end of last treatment**

The occurrence of CR, PR and SD after the end of treatment was considered to be disease control, and the absence of biochemical recurrence at the end of treatment of prostate cancer was considered to be disease control. Proportion of subjects with disease control 3 months after the end of the last radiation therapy.

Calculation formula: $DCR = \text{number of subjects under disease control} / \text{total number of subjects} \times 100\%$

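### SAP 5.4.1 does not say at what level two readers must agree, so a third reader can override two reads that already settle DCR or ORR

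*SAP*

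**What the plan says.** SAP 5.4.1 (Key Effectiveness Indicators) has two evaluators. If their efficacy results are consistent, that result stands. If not, "the independent evaluation value of the third evaluator will be taken as the final evaluation results". The third evaluator is not limited to choosing between the first two results. Neither consistent nor inconsistent is tied to the RECIST category or to the endpoint status.

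The endpoint itself is binary. SAP 2.1.1 states: "The occurrence of CR, PR and SD after the end of treatment was considered to be disease control". Success requires the Clopper-Pearson interval to clear the target: "if the lower limit of the 95% confidence interval of the test results was greater than 80" percent.

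Protocol 3.1.4.1 adds a step that is absent from the SAP's endpoint, missing-data and analysis sections. PD found at the 3-month imaging must be checked by PET-CT, and if progression cannot be confirmed the subject is recorded as SD. In the SAP, PET appears only in the abbreviation list. Neither document says whose PD reading triggers PET-CT, or whether PET-CT comes before or after the readers' results are reconciled.

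**The concern.** The Protocol has the panel read by RECIST 1.1, whose results are CR, PR, SD and PD, so comparing categories is the natural reading of SAP 5.4.1. On that reading, a split within CR/PR/SD goes to a third reader although it cannot affect DCR. Both reads already say controlled, so the third read can change DCR in one direction only, towards failure. One reader then outweighs two who agree on the endpoint.

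ORR has the mirror problem. SD and PD are both non-response, yet a third read of PR makes the subject a responder, and a PR triggers no PET-CT.

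The margin is thin: at 42 evaluable subjects the success rule tolerates three failures. A third-reader PD also sends the subject to PET-CT over a disagreement that the endpoint did not need resolved.

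**Working it through.** **Inputs from the documents.** Target and alpha: "the target value is set at 80%, and the bilateral significance level is 0.05" (Protocol 4.2.1). Expected rate: "experimental medical devices should be at least 80%, and the expected value should be 95" percent (Protocol 3.1.2). Power 80% (Protocol 4.3). Size: "the test group needs a sample size of at least 42 cases", with about 10% dropout (Protocol 4.2.1).

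**The plan's own figure.** n = [(1.960·√(0.80·0.20) + 0.842·√(0.95·0.05)) / 0.15]² = 41.59, so 42; 42/0.90 = 46.7, so 47. Both reproduce.

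**The success rule at n = 42.** The Clopper-Pearson lower limit is 80.52% for 39/42 and 77.38% for 38/42. Success therefore needs at least 39 controlled. Exact power at a true 95% is P(X ≥ 39) = 84.3%; exact type I error at 80% is 0.0208.

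**Assumptions, not in the documents.** Readers err independently. On a truly stable tumour each calls PD with probability p, PR with probability q, and SD with s = 1 − p − q. A true PD is misread only as SD, with probability p. PET-CT reverses a share c of false PD results.

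**False PD on a stable tumour.**
- Category rule: F₁ = p² + [1 − (p² + q² + s²)]·p
- Majority on controlled/not controlled: F₂ = p²(3 − 2p)
- Difference: F₁ − F₂ = 2pqs, which is exactly the case of an SD/PR split followed by a third read of PD.

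For p = 0.05, q = 0.20, s = 0.75: F₁ = 0.0025 + 0.395·0.05 = 0.02225; F₂ = 0.0025·2.9 = 0.00725; difference 2·0.05·0.20·0.75 = 0.015.

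**Effect on power.** Observed DCR = 0.95·[1 − F(1 − c)] + 0.05·p²(3 − 2p). The last term is true PD missed, equal under both rules here. For p = 5%, q = 20%, c = 0 this gives 92.9% against 94.4%. Power is P(X ≥ 39 of 42), shown as category rule / majority rule:

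| p, q | F₁ / F₂ | c = 0 | c = 50% | c = 80% | c = 100% |
|---|---|---|---|---|---|
| 5%, 20% | 2.225% / 0.725% | 65.4 / 78.8 | 75.5 / 81.8 | 81.1 / 83.5 | 84.6 / 84.6 |
| 2%, 20% | 0.742% / 0.118% | 78.4 / 83.5 | 81.5 / 83.9 | 83.2 / 84.2 | 84.4 / 84.4 |
| 1%, 10% | 0.208% / 0.030% | 82.7 / 84.1 | 83.5 / 84.2 | 84.0 / 84.3 | 84.3 / 84.3 |

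**Cross-check on this route alone.** Let d be the share of controlled tumours with a within-controlled split and f the chance that the third reader then calls PD. With d = 2qs = 30% and f = p = 5%, DCR = 0.95·(1 − 0.015) = 93.6% and power is 71.7% against 84.3%; with half reversed it is 78.3%. With d = 20%, f = 2% and no reversal it is 81.2%.

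**ORR, same assumptions.** For a stable tumour with p = 0.05, q = 0.20, false response is q² + 0.395·q = 0.040 + 0.079 = 11.9% under the category rule, and q²(3 − 2q) = 0.04·2.6 = 10.4% under a response/no-response majority.

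**Cost of the alternative.** If true PD is misread as SD 4% and as PR 1% of the time, the category rule detects 0.95² + 0.0958·0.95 = 99.35% of true PD and the majority rule 0.9025·1.1 = 99.28%. With 15% and 5% it is 90.8% against 89.6%.

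**The case against.** The strongest objection is the PET-CT step. Under Protocol 3.1.4.1 a third-reader PD at 3 months is not the last word, because unconfirmed PD is recorded as SD and so counts as controlled. This stands, and it limits the finding. A reader might infer from SAP 5.4.1 alone that one reader's PD automatically becomes a failure; the Protocol does not support that. The step does not close the gap, though. The SAP omits it, so a programmer working from SAP 5.4.1 would take the third read as final. Its order relative to reader reconciliation is unstated, and it does nothing for a third-reader PR in ORR.

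Second, if consistency were meant at endpoint level, SD against PR would be consistent and no third read would follow. The text allows that, which is why the finding is conditional. It also shows how small the fix is: where two readers differ on controlled status, the third reader's status already is the majority.

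Third, the error rates are assumed and the upper end is high: p = 5%, q = 20% means category disagreement in 39.5% of stable tumours. Readers view the same scans, so independence is doubtful. The Protocol does not call 95% an error-free rate, so subtracting reader error may count some of it twice. Prostate subjects without biochemical recurrence are classed as controlled without this route. All of this stands, and only a range can be given.

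Fourth, a third-reader PD may be correct, and the present rule is slightly more sensitive if PD is sometimes misread as PR. This also stands.

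**Conclusion.** The concern holds in conditional form. SAP 5.4.1 leaves the level of agreement undefined. On the category reading it lets one reader override two who agree on the endpoint, which can add false failures to the 3-month DCR unless PET-CT reverses them, and can add false responders to ORR with no such check.

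At 42 evaluable subjects the power loss is about 1 point (p = 1%, q = 10%) to 13 points (p = 5%, q = 20%) with no PET-CT reversal. With half of false PD reversed it is about 1 to 6 points, and with full reversal it is zero. These figures rest on independent readers and on error and reversal rates that the documents do not give; the 13 points are the top of an assumed range and not a forecast.

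A reader might also infer that the rule favours the device. It does not on the primary endpoint: the extra calls are failures, so they lower power and do not inflate type I error. ORR can move in the device's favour, but it is a secondary estimate with no success threshold. The point should be settled before database lock because the margin is three failures and the correction is nearly free.

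**What to change.** In SAP 5.4.1, with a matching line in 5.4.2 for ORR:

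- For DCR, judge reader agreement on controlled (CR/PR/SD) versus not controlled (PD). For ORR, judge it on response (CR/PR) versus no response (SD/PD).
- If the first two readers agree on that status, it is final. If they do not, the two-of-three majority including the third reader is final.
- Keep the RECIST category for description only.
- Reconcile the SAP with Protocol 3.1.4.1: state whose PD reading triggers PET-CT confirmation, and how the reconciled reading and the PET-CT recoding combine into the analysed result.

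The cost is SAP wording and the derivation program; no extra reader or read is needed. The one statistical downside is slightly lower detection of true PD if PD is sometimes misread as PR (99.28% against 99.35% in the 4%/1% example).
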